# **5.** Randomisation and enrolment

Enrolment will take place in a location within primary care, in which the Symptoms Clinic will also be held, by CRN or practice research nurses. The research nurse or delegated member of the research team will discuss the study with the patient, complete the informed consent process and collect baseline data. It must be made completely and unambiguously clear that participation in the study is entirely voluntary and that consent to participate in the study can be withdrawn at any time without affecting their future care.

The research nurse taking consent will ensure that the participant has a copy of the PIS and will also provide the participants with a copy of the completed consent form. The original consent form will be filed in the Investigator Site File and a second copy will be kept with the participant's notes.

Randomisation will be completed after consent has been obtained and baseline data collected (details of baseline measures in section 7.4). Patients will be individually

randomised (1:1) and will be allocated to the Symptoms Clinic plus usual care or usual care alone using a computer generated pseudo-random list, stratified by study centre with random permuted blocks of varying sizes. Randomisation will be via SCRAM, the Sheffield CTRU-hosted web-based randomisation system and will be in accordance with their Standard Operating Procedures (SOPs). The sequences will be held on a secure server and will be concealed until recruitment, data collection and analyses are complete.

The research nurse or delegated member of the research team will enter the participant demographic details, PHQ-15 score and confirmation of consent directly into the randomisation system. If internet access is not available there will be a reserve method to contact the central trial team at the University of Sheffield by telephone and provide these details for a member of the core team to enter into the randomisation system. The research nurse will then inform the participant of their allocation, and if assigned to the intervention make a first appointment to attend the Symptoms clinic. All participants (intervention and control) will be advised to continue to use healthcare services as and when they deem appropriate. Sheffield CTRU will confirm the allocation and appointment details (if applicable) in a letter to the participant.

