# 8. Statistics

## 8.1 Sample size

## 8.1.1 Definition of effect size

In the pilot trial we observed an average 3.2 point clinically important change in the intervention group from baseline to 13 weeks, compared to a 1.4 point change in the control group. We have thus powered the trial on a between group difference of 2 points on PHQ-15 (equivalent to a clinically important 3 point change from baseline)

We have based calculations of effect size on a pooled standard deviation of 5; this is larger than that seen in our preliminary studies owing to their restricted eligibility range and more in keeping with observational studies. This results in a standardised effect size of 0.4, which is similar to that seen in two small European studies of extended GP consultations for broadly comparable patients [25, 26].

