## 8.2 Statistical analysis

Full details of all analyses will be provided in the Statistical Analysis Plan, which will be reviewed by the Trial Steering Committee (TSC) and the Data Monitoring and Ethics Committee (DMEC) prior to analysis.

The primary outcome will be analysed using a general linear model correcting for baseline PHQ-15. Secondary outcomes will be analysed in a similar manner within a generalised linear modelling framework using appropriate link functions for the outcomes' distributions. The primary outcome will be analysed using observed data with no imputation for missing data, but we will assess the amount and patterns of missing data and test the sensitivity of estimates of treatments effects using an appropriate imputation strategy. We will explore potential modification of the treatment effect by including treatment-by-subgroup interactions in models. All treatment effect estimates will be presented with 95% confidence intervals.

A single main analysis will be performed at the end of the trial when all follow up has been completed. Interim analyses will be performed if requested by the DMEC and Standard Operating Procedure (SOP) ST004 will be adhered to maintain the integrity of the trial.

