## Randomisation

The type of intervention included in each invitation pack (whether a brief PIS and/or a pen is to be included or not) will be determined by random allocation. Patients will be randomised in a 1:1:1:1 ratio, stratified by GP practice. Block randomisation with random varying block sizes will be used, with the block sizes being determined by a statistician and not shared with other researchers. The allocation lists will be generated by a CTRU statistician and shared only with the CTRU staff preparing the invitation packs, who will be independent of the CTRU staff who will process the invitation responses. All recruitment materials will be placed in sealed envelopes which will be pre-stamped, ready for the practice to post out to patients. The packs will be placed in order of the random allocation list and then numbered sequentially before being sent to the practice. By numbering the packs, the researcher will have a record of which interventions are in each pack, which will enable the trial team to monitor if packs are sent out in the correct randomised order. Practice staff will be informed to label the sealed recruitment packs with patient addresses in the sequential order that the researcher had placed them in. Patients will not know that they are part of a trial testing recruitment interventions so will be blind to the SWAT hypothesis. CTRU staff undertaking trial recruitment will be blind to the group to which patients are allocated. It will not be possible to entirely blind practice staff to the interventions as it will be clear that some packs have pens in and some do not.

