## Statistical analyses

Analyses will be conducted on an intention to treat basis, including all randomised participants on the basis of the groups to which they were randomised. Analysis will be conducted using 2 sided significance tests at the 5% significance level. For analysis of the primary outcome, logistic regression will be used to produce odds ratios and their associated 95% confidence intervals and p-values. Cost effectiveness will be presented as a cost-per-additional recruited participant.

Results from this SWAT will ultimately be combined in a meta-analysis with response rate data from other host trials participating in the PROMETHEUS study.

Anonymised data from MSS3 will be sent to the PROMETHEUS study team in accordance with the PROMETHEUS study data sharing agreement (Appendix E).

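### Section 8.2 does not name study centre, the sole stratification factor, in the primary model; followed as written, the reported standard error is slightly too large if centre is prognostic

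*Protocol*

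**What the plan says.** Section 5 of the protocol allocates participants individually, 1:1, from a list that is "stratified by study centre with random permuted blocks of varying sizes". There are three centres, and no other stratification factor is given.

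Section 8.1.1 states that the sponsor "powered the trial on a between group difference of 2 points on PHQ-15", with a pooled standard deviation of 5. Section 8.1.2 allows for 25% loss to follow-up and adds 6% for small imbalances or differences between treatment centres, giving 188 per arm.

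Section 8.2 then states: "The primary outcome will be analysed using a general linear model correcting for baseline PHQ-15". Secondary outcomes are to be handled similarly, within a generalised linear modelling framework. Centre is not mentioned in that section, which also says: "Full details of all analyses will be provided in the Statistical Analysis Plan".

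**The concern.** Blocking within centre makes the arms nearly equal in size at each centre, so differences between centres largely cancel out of the treatment comparison. A model without centre does not know this. It leaves the between-centre variation in the residual and computes a standard error as if that variation could still fall unevenly between the arms. The estimate is then somewhat more precise than its reported standard error, the confidence interval is wider than it needs to be, and the test rejects less often than 5% under the null.

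The design treats centre as worth attention twice, in the stratification and in the 6% inflation, while the stated model does not use it. Each centre has its own two extended-role GPs and its own recruiting practices, so some difference in outcome between centres is plausible. Because secondary outcomes follow the primary approach, the omission would carry over to them.

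**Working it through.** **Inputs from the protocol.** Difference 2 points and SD 5 (8.1.1); 90% power, alpha 0.05, 25% loss and 6% inflation (8.1.2); three centres, 1:1, permuted blocks within centre (section 5).

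**Assumed.** A two-sided test, since sidedness is not stated, and the share r of residual variance that lies between centres, which the documents do not give. The range shown for r is 0% to 10%. SD 5 is used as the residual SD, with no credit for baseline adjustment.

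**The plan's own figure.**
- Normal approximation: n = 2 × (1.960 + 1.282)² × 5² / 2² = 131.3, so 132 per arm. 132 × 1.06 / 0.75 = 186.6, so 187.
- t-based: 133 per arm. 133 × 1.06 / 0.75 = 187.97, so 188, which is the stated figure.
- Evaluable per arm: 188 × 0.75 = 141.

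**Effect of omitting centre.** With exact balance within centre:
- reported SE without centre = 5 × √(2/141) = 0.595;
- SE that matches the design = 0.595 × √(1 − r);
- overstatement = 1/√(1 − r) − 1;
- type I error without centre = 2 × [1 − Φ(1.960/√(1 − r))];
- power without centre = Φ[(2/0.595 − 1.960)/√(1 − r)];
- power with centre = Φ[2/(0.595 × √(1 − r)) − 1.960].

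| Centre share r | SE too large by | Type I error without centre | Power without centre | Power with centre |
|---|---|---|---|---|
| 0% | 0% | 0.050 | 91.9% | 91.9% |
| 1% | 0.5% | 0.049 | 92.0% | 92.2% |
| 2% | 1.0% | 0.048 | 92.1% | 92.4% |
| 5% | 2.6% | 0.044 | 92.4% | 93.1% |
| 10% | 5.4% | 0.039 | 93.0% | 94.3% |

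**Check by simulation.** Three centres (376 in total), blocks of 4, 6 or 8, 25% lost at random, baseline PHQ-15 in both models, 4000 runs per setting. The Monte Carlo error of a 5% rate is √(0.05 × 0.95/4000) = 0.0034.
- r = 5%: mean reported SE 0.597 without centre and 0.582 with it; type I error 0.039 and 0.047. The actual spread of the estimates was 0.576–0.588 without centre and 0.572–0.584 with it.
- r = 10%: mean reported SE 0.597 and 0.567; type I error 0.042 and 0.050. The actual spread was 0.583–0.586 and 0.576.

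The direction agrees with the formulas. The formulas assume exact balance within centre at analysis. Losses to follow-up loosen that balance, so the table is best read as the outer edge of the effect for a given r.

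**Check in PHQ-15 points.** Assume a baseline correlation of 0.5, so the residual variance is 25 × 0.75 = 18.75, and a between-centre SD of 1.0 or 1.5. With three centres, about two-thirds of the between-centre variance is expected in the residual.
- With centre: √(2 × 18.75/141) = 0.516.
- Without centre, SD 1.0: √(2 × 19.42/141) = 0.525, about 2% larger.
- Without centre, SD 1.5: √(2 × 20.25/141) = 0.536, about 4% larger; type I error 2 × [1 − Φ(1.960 × 0.536/0.516)] ≈ 0.042.

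These correspond to r = 0.67/19.42 = 3.4% and r = 1.5/20.25 = 7.4%, inside the range of the table.

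**The case against.** The strongest objection is that 8.2 does not say baseline PHQ-15 is the only covariate. A reader might infer that centre is excluded, but the text does not support that. Full details are deferred to the statistical analysis plan, which could add centre without contradicting anything in 8.2. This stands, and it limits the point to the model as the protocol words it. It does not remove the point, because 8.2 goes as far as naming a covariate and leaves out the one factor that the randomisation was built on.

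Second, the 6% inflation can be read as the sponsor's allowance for exactly this cost and not as a contradiction. That also stands. It lifts 133 evaluable per arm to 141, which is why power stays above 90% in every row of the table.

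Third, centre may hardly matter. All centres recruit on the same screening PHQ-15 range of 10 to 20, and the model adjusts for baseline. A between-centre SD of 1.5 would be 2.25/25 = 9% of the planning variance, which may be generous. At a 1% to 2% share the standard error is only 0.5% to 1.0% too large, and at 0% the effect disappears.

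Fourth, a reader might extend the point to the embedded recruitment study in Appendix 1, where "Patients will be randomised in a 1:1:1:1 ratio, stratified by GP practice" and, for analysis, "logistic regression will be used to produce odds ratios and their associated 95% confidence intervals and p-values". That analysis paragraph names no model terms at all, not even the two recruitment factors. It is therefore silent on practice and does not specify an unadjusted model. No between-practice variation is given, so no effect can be computed. At most this is a minor clarification, and it is not part of the point made here.

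**Conclusion.** The point holds as a small matter of precision and consistency. As worded, the primary model does not reflect the stratified design. If centre is prognostic, the reported standard error is up to about 5% too large and the type I error falls as low as 0.039, over an assumed centre share of 0% to 10%. Naming centre gains at most 94.3 − 93.0 = 1.3 points of power.

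Two stronger readings are not supported. One is that the primary confidence interval is unreliable because its coverage is not nominal. The departure is towards over-coverage: the estimate is unbiased and false positives are not inflated. The other is that the benefit of stratifying is thrown away. In the simulation the estimates varied almost as little without centre as with it, so most of the benefit is kept and the reported standard error merely fails to show it.

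The size rests wholly on the assumed centre share. Whether the gap exists in the final analysis depends on a statistical analysis plan that is not shown.

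**What to change.** In section 8.2, describe the primary analysis as a *general linear model adjusting for baseline PHQ-15 and study centre (stratification factor, fixed effect)*, and carry centre into the secondary models. A fixed effect is preferable because three centres are too few to estimate a between-centre variance well.

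Centre is already recorded for the stratified allocation, so no new data are needed. The primary model loses two degrees of freedom out of about 279 (2 × 141 evaluable participants less three parameters). The sample size of 188 per arm is unchanged. If the statistical analysis plan already includes centre, the change only brings the protocol wording into line with it.

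Optionally, Appendix 1 could state whether practice enters the logistic model. Conditioning on practice, or giving it a random effect, yields a conditional odds ratio and not a marginal one. That choice should be made with the planned meta-analysis across host trials in mind.

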# 9. Safety assessments

There are a number of anticipated adverse events due to the nature of the participant group being studied. The participant group are regular users of healthcare resources and may be frequently referred to specialist services or undergo investigational tests. Current mental health illness and previous trauma are prevalent in patients with Persistent Physical Symptoms, and there is some potential for the intervention to temporarily exacerbate mental distress. However in our previous feasibility study we found no major unexpected changes in physical or mental health [19].

# 9.1 Definitions

## Adverse event (AE)

A standard definition of an AE is "any untoward medical occurrence in a study participant".

The MSS3 patient population – who by definition have multiple symptoms and at least moderate healthcare use - are likely to experience many 'medical occurrences'. It is difficult to identify which medical occurrences are 'untoward' but fall short of the serious adverse event criteria. The multiple and complex symptoms of this population mean that the link of causality between the intervention and the event will be difficult to interpret. In addition, due

to the data collection methods employed in the trial, we anticipate differential identification of adverse events between arms, as those attending the symptoms clinics will be having regular contact with a GP over the first months of the trial. We expect any non-serious adverse events reported via participant-completed questionnaires or contained in GP records to be less reliable than those collected by the ER-GP and contain incomplete information.

For this study we therefore consider the collection of all non-serious adverse events both problematic and of limited utility. We will therefore only collect the following AEs: (a) significant exacerbation of mental distress defined as a PHQ-9 score of 20 or more and/or a score of 2 or 3 on question 9 (suicidality item), representing at least a 1 point score change (i.e a change from 2 to 3 from their previous measure)

(b) self-harm, which may be identified by the ER-GP during consultations or where volunteered by the participant to a member of the research team or through review of medical notes

(c) any emerging serious mental illness or substance use disorder identified after randomisation

## Serious Adverse Event (SAE)

An SAE is an event that:

- (a) results in death;
- (b) is life-threatening\* (subject at immediate risk of death);
- (c) requires hospitalisation or prolongation of existing hospitalisation\*\*;
- (d) results in persistent or significant disability or incapacity;
- (e) consists of a congenital anomaly or birth defect
- (f) is otherwise considered medically significant by the investigator\*\*\*

\* 'life-threatening' in the definition of 'serious' refers to an event in which the patient was at risk of death at the time of the event; it does not refer to an event which hypothetically might have caused death if it were more severe.

\*\*Hospitalisation is defined as an inpatient admission, regardless of length of stay, even if the hospitalisation is a precautionary measure for continued observation. Hospitalisations for a pre-existing condition, including elective procedures that have not worsened, do not constitute an SAE.

\*\*\*Other important medical events that may not result in death, be life-threatening, or require hospitalisation may be considered a serious adverse event/experience when, based upon appropriate medical judgement, they may jeopardise the patient and may require medical or surgical intervention to prevent one of the outcomes listed in this definition.

## **Expected SAEs**

Serious adverse events that are expected or have the potential to be experienced by the patient population: (a) diagnosis of cancer, (b) diagnosis of a serious medical condition, (c) admission to hospital with an exacerbation of persistent physical symptoms (d) self-harm (resulting in hospitalisation or otherwise meeting the definition of a serious adverse event); (e) suicide attempt; (f) death from suicide.

### **Related Unexpected SAEs**

These are SAEs that have not been listed in this protocol as expected and are suspected to be "related" to any aspect of the research procedures.

## 9.2 AE and SAE identification

There a number of routes through which an AE or SAE may be identified, these include:

- Participant self-report
- Health resource use data collection
- ER-GP identification

### Participant Self-report

Self-report questionnaires will be collected at baseline, 13 weeks, 26 weeks and 52 weeks post randomisation. The PHQ-9 will identify exacerbation of mental distress and current suicidal thoughts. If a patient scores 3 on question 9 of the PHQ-9 at baseline then they will not be randomised in to the study and the suicide protocol will be triggered. This can be triggered at any point during the study if a score of 3 is identified and the event will be reported as an AE. The health resource use questionnaire will include questions about A&E attendance and hospital admissions.

Whilst it is unlikely that participants will report SAEs between data collection points they will be provided with contact details of the CTRU research team on which they can contact to inform them of an event.

Self-reported SAEs will be flagged to the Trial Manager (or delegated member of staff in the absence of the Trial Manager). The patient completed PHQ-9 and SAE data will be monitored by the CTRU research team to allow efficient identification and reporting of events. Where an event has been identified by the CTRU research team but more information is required they will contact the participant (by telephone in the first instance) to obtain more detailed information about the event.

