#### Intervention

The Symptoms Clinic is an extended-role GP intervention which has gone through several stages of development and piloting. The Symptoms Clinic is a locality based service delivered by specially trained GPs which uses a psychologically-informed medical consultation model developed for patients with persistent physical symptoms. The clinics are designed to allow patients to describe the nature and impact of their symptoms and help them find new ways of understanding and managing those symptoms drawing on current scientific knowledge. Each patient receives one 50 minute consultation and up to three structured 15 minute follow-ups.

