## Exclusion criteria:

Patients will be excluded if any of the following apply:

- 1. A score of 3 on question 9 on the PHQ-9 completed at the baseline visit\*
- 2. Difficulty conducting a healthcare consultation in English without either a professional or family interpreter or other assistance (either indicated in GP records, or becoming apparent during the enrolment and consent process)
- 3. The GP regards inviting them to participate as inappropriate (e.g. recent bereavement)
- 4. Severe symptom-related disability (e.g. requiring help with daily personal care or severely impaired mobility)
- 5. Undergoing active multidisciplinary rehabilitation, IAPT programme or specialist psychological treatment including specialist pain, fatigue or other symptom clinic at the time of screening.
- 6. Currently pregnant\*\* or less than 6 months postnatal at the time of the screening telephone call

\*If a score of 3 is identified at any time point during the study the suicide protocol will be triggered

\*\*if a participant becomes pregnant after the screening telephone call they will remain in the study and continue to attend the Symptoms Clinic Intervention if allocated to the intervention group.

Following stages 1-3, the details of interested and potentially eligible patients will be passed on to a local research nurse who will contact the patient to discuss the study further, answer any questions from the patient and discuss a timetable for further participation. If a potential participant wishes to proceed, the research nurse will complete screening checks by enquiring directly about the exclusion criteria relating to personal care, active multidisciplinary rehabilitation, and current specialist psychological treatment. When discussions are complete the researcher will make an appointment with the patient for study enrolment. If the patient wishes to have more time to consider participation then a second phone call can be arranged.

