## ER-GP identification

During a Symptoms Clinic consultation an ER-GP may identify an AE or SAE through the participant's account of recent clinical events or through their expressed concerns. ER-GPs

<sup>1 E.g. Abdominal pain admission in a patient with Irritable Bowel Syndrome or a neurological admission in a patient with functional neurological symptoms.

will use their clinical experience to assess and manage changes in patients' clinical conditions, working within the policies of the study.

If the ER-GP has a concern for the mental distress of a participant they will administer the PHQ-9 to determine if the participant meets the threshold for an adverse event.

The ER-GP will be trained in what constitutes an AE and SAE.

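### The mental-distress adverse event is defined inconsistently, and its count pooled over all detection routes is not comparable between arms

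*Protocol*

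**What the plan says.** Section 9.1 limits the non-serious adverse events to three kinds. Item (a) is "significant exacerbation of mental distress defined as a PHQ-9 score of 20 or more and/or a score of 2 or 3 on question 9", qualified as "representing at least a 1 point score change (i.e a change from 2 to 3 from their previous measure".

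Section 9.2 (Participant Self-report) deals with a question-9 score of 3 at any time in the study and sets no change condition: "if a score of 3 is identified and the event will be reported as an AE". The same paragraph opens with "Self-report questionnaires will be collected at baseline, 13 weeks, 26 weeks and 52 weeks post randomisation" and continues "The PHQ-9 will identify exacerbation of mental distress and current suicidal thoughts". In Table 1 (section 7.4) the PHQ-9 is ticked at recruitment, 13 weeks and 52 weeks, and its 26-week cell is empty.

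Section 9.2 (ER-GP identification) adds another source. When the extended-role GP is concerned about a participant's mental distress, "they will administer the PHQ-9 to determine if the participant meets the threshold for an adverse event". Only the clinic arm has these consultations: one long first visit and, per the Trial Summary, "up to three structured 15 minute follow-ups".

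One exclusion criterion also matters here: "A score of 3 on question 9 on the PHQ-9 completed at the baseline visit". No randomised patient can start at 3.

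**The concern.** Section 9 recognises that the intervention may cause a short-lived worsening of distress, so item (a) is the non-serious harm that bears most directly on it. The count should depend on what happened to patients, and two features make it depend on other things.

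First, two people coding the same questionnaires can reach different totals, depending on whether they follow 9.1 or 9.2 and on how they read the example in 9.1.

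Second, one arm has PHQ-9 assessments that the other cannot have. Section 9.1 says that events are expected to be picked up unequally in the two arms and gives this as one reason for restricting collection. The event it retains still has an unequal route. Those extra assessments are also measures, so they can become the reference from which a later scheduled score is judged to have changed.

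**Working it through.** The protocol gives no rate for this event, so there is no stated figure to reproduce. The check compares the rules, then the routes, then gives an illustration.

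**1. The two rules on scheduled PHQ-9s.** Baseline question 9 can be 0 to 2 (3 is excluded); weeks 13 and 52 can be 0 to 3. That gives 3 × 4 × 4 = 48 paths. Change is read as a rise, because item (a) concerns exacerbation.

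| Previous → current | 9.1, rise of at least 1 | 9.1, example read literally | 9.2 |
|---|---|---|---|
| 0 or 1 → 2 | event | no event | silent |
| 0 or 1 → 3 | event | no event | event |
| 2 → 3 | event | event | event |
| 3 → 3 (weeks 13 to 52 only) | no event | no event | event |

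At week 13 every 3 is a rise, so both rules count it. The only scheduled score of 3 that 9.2 counts and the 9.1 change rule does not is the unchanged 3 at week 52. Section 9.2 does not mention a score of 2, which is not a contradiction. The example in 9.1 is introduced as a definition (i.e.). Taken literally, no score of 2 could ever qualify, although the same sentence lists 2. It is also unclear whether the change condition applies to a total of 20 or more.

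**2. Scheduled looks.** After baseline there are two in each arm, at weeks 13 and 52, with 52 − 13 = 39 weeks between them.

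**3. Extra looks.** Clinic arm only: at most 1 + 3 = 4 visits, with a PHQ-9 only where there is concern. Take the same true question-9 course at baseline, at an intermediate time and at week 13. Suppose that an extra PHQ-9 is given at the intermediate time in the clinic arm.

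| True course | Usual care, 9.1 | Clinic arm, 9.1 | Effect |
|---|---|---|---|
| 0, 3, 0 | 0 events | 1, at the clinic | event added |
| 0, 3, 3 | 1, at week 13 | 1, at the clinic; week 13 shows no rise | pooled count equal, scheduled count one lower |
| 2, 1, 2 | 0 (2 to 2) | 1, at week 13 (1 to 2) | event added to the scheduled count |

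Under 9.2 the second course gives one event in usual care and two in the clinic arm.

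**4. Illustration of size (assumed inputs).** Let p be the chance that any one look is positive, equal in both arms and independent between looks, and let k be the average number of extra looks. The proportion with at least one event is 1 − (1 − p)² in usual care and 1 − (1 − p)^(2 + k) in the clinic arm. With 188 per arm (section 8.1.2) and p = 0.05, usual care gives 1 − 0.95² = 9.8%, about 18 patients.

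| k | Clinic arm, p = 0.05 | Patients of 188 | Ratio, p = 0.02 | Ratio, p = 0.05 | Ratio, p = 0.10 |
|---|---|---|---|---|---|
| 0.5 | 12.0% | 23 | 1.24 | 1.23 | 1.22 |
| 1 | 14.3% | 27 | 1.49 | 1.46 | 1.43 |
| 2 | 18.6% | 35 | 1.96 | 1.90 | 1.81 |
| 4 (ceiling) | 26.5% | 50 | 2.88 | 2.72 | 2.47 |

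Neither p nor k is in the protocol. Independence ignores persistent distress, where an extra look moves an event earlier instead of adding one. A look prompted by concern may be positive more often than a routine one. These two departures pull in opposite directions, so the table shows how the mechanism works and does not estimate its size.

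**The case against.** **The conflict between 9.1 and 9.2 is narrow and affects both arms alike.** This stands. A reader might infer that it makes the arms non-comparable, and it does not. One can add that 9.1 is the definition, that 9.3 records events as the protocol defines them, and that the sentence in 9.2 is mainly about triggering the suicide protocol. But that sentence also says the score is reported as an adverse event, so the text needs one rule.

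**The 26-week point is not a contradiction.** This also stands. A reader might infer from 9.2 that a PHQ-9 is promised at 26 weeks. The text says only that questionnaires are collected then. Table 1 bears that out with the PHQ-15, EQ-5D-5L and self-reported healthcare use, and it settles the PHQ-9 schedule. Nor are the 39 weeks free of all surveillance: participants hold contact details for the trial team, and self-harm is also sought in medical notes.

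**Unequal detection is disclosed, and section 8.2 prescribes no between-arm test of adverse events.** True. The method of comparison may be in the SAP, which was not available here, and the adverse event form is not shown, so it may already record the route. Disclosure does not remove the effect, however. The definition, the reference to a previous measure and the clinic-only route are all fixed in the protocol, and section 11.3 sends safety data to the monitoring committee.

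**The bias may be small, because an extra look can bring an event forward instead of adding one.** Correct for persistent distress, as the second course in the working shows. It does not hold for transient distress, which is the kind section 9 anticipates.

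**Conclusion.** The point holds in a limited form. Item (a) has inconsistent counting rules. The practical divergence on scheduled PHQ-9s is one path (3 at week 13, still 3 at week 52), plus the ambiguity created by the example in 9.1. That is a defect of definition and not a source of imbalance.

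The imbalance comes only from the concern-triggered clinic PHQ-9. Because of it, counts pooled over all routes cannot be compared between arms. Because change is measured from the previous measure, whichever that was, even the week-13 and week-52 counts in the clinic arm can be altered unless the reference is fixed.

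A reader might go further and conclude that clinic-arm rates are certainly inflated, or by a given amount. The documents do not support that. Inflation is likely, but resetting the reference can lower the scheduled count as well as raise it. Four extra looks is a ceiling and every rate used above is assumed. Nor are scheduled scores beyond use: with change taken from the last scheduled PHQ-9 they are ascertained at the same times in both arms.

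This should be corrected, though it does not touch the primary analysis.

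**What to change.** 1. Reconcile sections 9.1 and 9.2 into one counting rule for question 9. State whether an unchanged 3 is a new event, remove the conflict between the example and the threshold of 2 or 3, and say whether the change condition applies to the total score. Which rule to adopt is for the investigators.
2. Record the identification route for every item (a) event (scheduled questionnaire, ER-GP, other), if the form does not already do so.
3. Base any between-arm comparison of item (a) on the PHQ-9s scheduled in both arms (13 and 52 weeks per Table 1), with change measured from the last scheduled PHQ-9. List ER-GP-identified events separately.
4. As a minor wording point, state in 9.2 that the PHQ-9 is not among the 26-week questionnaires, in line with Table 1.

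The cost is protocol wording and at most one field on a form. The scheduled comparison uses questionnaires already collected, so no visit, questionnaire or staff time is added. The ER-GP's assessment and the suicide protocol are unchanged.
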